9.6 DATA MANAGEMENT

Data are provided as electrical data formatted csv by MDV and stored and managed in Milliman Inc.

SAS and Microsoft Excel are used for statistics.

9.7 DATA ANALYSIS

9.7.1 Main analysis

Propensity Score Matching

[figure not shown]
To reduce channelling bias, dabigatran and warfarin study groups will be established using PS matching method, on a 1:1 fixed ratio. The nearest neighbour method of propensity score matching within a caliper of 0.10 of the standard deviation of the estimated logit will be used to select the matched samples. All pre-defined variables has been evaluated in CTMS 1160.279 for inclusion into the model. Covariates with less than 10 patients present in the data was eliminated as well as CHADs which showed high co-linearity with CHADsVASC which was eliminated from the model. Otherwise, all pre-defined variables will be used. For further detail of the methodology of PS matching, please see the study protocol CTMS 1160.279.

For the primary outcome

Incidence rates of each treatment cohort (warfarin and dabigatran) will be provided, and all analysis will be conducted on the PS matched sample. The hazard ratio (HR) of stroke/systemic embolism for the dabigatran cohort as compared to the warfarin cohort and its 95% confidence interval (CI) will be estimated from the PS matched cohort using a Cox regression model with treatment group as the dependent variable. No additional covariates are considered in the Cox model as no residual imbalance was identified after PS matching (1160.276 study report, c15432368)." There will be no formal hypothesis testing. Kaplan Meier analysis with the number of patients at risk during the follow-up period after the index date and the number of events for ischemic stroke and major bleeding will be provided.

For the secondary outcome

Same analysis method will be utilized to calculate HR for the outcome of major bleeding.

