| Data sources: MDV clinical database. The database is health insurance claims database. As of end of February 2016, MDV provides commercial | | | |

| | | | |
|---|---|---|---|
| Name of company: Boehringer Ingelheim | | | |
| Name of finished medicinal product: Prazaxa | | | |
| Name of active ingredient: Dabigatran etexilate | | | |
| Protocol date: 6 Jul 2017 | Study number: 1160.0288 | Version/Revision: Version 1.0 | Version/Revision date: Not applicable |
| claims for in and out-patients consisting of medical records from more than 12.94 million patients from 230 large acute care DPC hospitals. . Observation period is planned from 14 March 2010 to 30 June 2016 considering the launch date of dabigatran. | | | |
| Study size: | The previous study 1160.279 was a feasibility study to look into the treatment pattern of OACs in Japan and internal validity of MDV database including availability of co-variates to conduct 1:1 PS matching. For warfarin and dabigatran comparison, the number of AF patients meeting inclusion and exclusion criteria after matching was 4,427 in each cohort. | | |
| Data analysis: | 
This study plans no formal hypothesis testing. The planned analyses are descriptive in nature and results are to be interpreted in an exploratory manner.
 
1:1 Propensity score matching (PSM) was conducted to address potential channelling bias. Outcomes will be assessed in the PSM sample.
 
Patient characteristics prior to and after propensity score matching will be described stratified by treatment group.
 
Patients will be followed up from treatment initiation (index date) to the day of treatment discontinuation (defined as a treatment gap longer than 14 days past the number of days of supply of the last prescription), the day before a switch to a different anticoagulant, the date of disenrollment in MDV, the end of the study period, the occurrence of the event of interest, or death of the patient, whichever occurs first (as-treated analysis).
 
Number of observed events, number of patient years, the corresponding incidence rates and their 95% confidence intervals (CIs) will be reported.
 
Dabigatran and warfarin outcomes will be compared by estimating the hazard ratios (HRs) for the outcomes and their CIs using Cox regression.
 
Kaplan-Meier curves for event-free survival will be estimated.
 | | |

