8. RESEARCH QUESTION AND OBJECTIVES

The primary objective is to compare the effectiveness (incidence of stroke/SE) in Japanese patients with atrial fibrillation and newly treated with either dabigatran or warfarin.

The secondary objective is to compare safety (incidence of major bleeding) in patients with atrial fibrillation and newly treated with dabigatran and warfarin in the real world Japanese setting using a claims database.

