9. RESEARCH METHODS

9.1 STUDY DESIGN

Study design

- Non-interventional new user cohort study based on existing data (Medical Data Vision (MDV) database) using propensity score matching

Treatments Considered:

- Dabigatran and warfarin

Strength of the study design

- Channelling bias as well as differences in baseline risk of outcome occurrence between treatment groups will be addressed by the use of propensity score (PS) matching

Outcomes

- Primary outcome: stroke and systemic embolism
- Secondary outcome: major bleeding defined by any bleeding event associated with hospitalization claims and/or transfusion claims

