9.3.2 Outcomes

9.3.2.1 Primary Outcome

- Outcome name: stroke and systemic embolism
- Time frame: drug exposure period
- Safety issue. N/A
- Definition: definition of stroke and systemic embolism provided in Koretsune et al will be used for this study⁸ as following.
 - ✓ Stroke: all three following conditions must be met:
 - [1] Imaging (magnetic resonance imaging (MRI) or computed tomography (CT)) is performed after a diagnosis code of atrial fibrillation.
 - [2] Diagnosis of stroke defined as I60-I64 occurs in the same month as the imaging
 - [3] Either of the following condition is met:
 - A) Rehabilitation for cerebrovascular disease within 30 days from the date of imaging
 - B) Death within 30 days from the date of imaging
 - ✓ Systemic embolism events:
 1. Retinal vascular occlusions: three following conditions must be met:
 - [1] Ophthalmic examination is performed after the date of definitive diagnosis of atrial fibrillation or cardioembolic stroke (including the day of the diagnosis).
The second or later ophthalmic examination during the same hospitalization is excluded.
 - [2] Diagnosis of retinal vascular occlusion in the month of the date of ophthalmic examination.
 - [3] The following A) and B) are satisfied:
 - A) Prescription of anticoagulant/antiplatelet agents on the day of ophthalmic examination or the next day
 - B) Non-prescription of anticoagulant/antiplatelet agents within 30 days from the date of ophthalmic examination.
 2. Other than retinal vascular occlusions: four following conditions must be met:
 - [1] Imaging: MRI, CT, roentgenography (using a contrast medium) or vascular echo is performed after the date of definitive diagnosis of atrial fibrillation or cardioembolic stroke (including the day of the diagnosis).
 - [2] Systemic embolism (including the name of injury/disease at the time of admission) is diagnosed and recorded as the name of the disease during hospitalization in the month of the date of imaging.
 - [3] The date of imaging or the next day: Treatment
Either of the following conditions is satisfied:
 - A) Treatment with heparin at >5,000 units or thrombectomy on the day of imaging or the next day
 - B) Death within 30 days from the date of imaging

✓ [4] Fees for emergency medicine administration or specific intensive care management on the day of imaging are calculated.

Intracranial bleeding: all four following conditions must be met:

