9.3.2.2 Secondary Outcome

- Outcome name: Major bleeding
- Time frame: drug exposure period
- Safety issue. N/A
- Definition: major bleeding is defined as any bleeding associated with hospitalization and/or blood transfusion (defined as MDV procedure code K920) claims. Bleeding will include the following diagnostic names with ICD 10 codes in the parenthesis, and the list is inclusive, not exclusive;
 - ✓ Subarachnoid hemorrhage (I60)
 - ✓ Intracerebral hemorrhage (I61)
 - ✓ Digestive tract hemorrhage (K922, K290)
 - ✓ Hemorrhage, not elsewhere (R58)
 - ✓ Intraocular Hemorrhage (H113, H313, H356, H431)

- ✓ Hematuria (R31, N028, N029)
- ✓ Excessive Menstruation, Hemorrhage from Uterus (N93)
- ✓ Hemathrosis (M250)
- ✓ Hemopericardium (I312)
- ✓ Hemoptysis, bleeding from airway (R04)
- ✓ Hematemesis (K920)
- ✓ Epistaxis (R040)
- ✓ Acute post-hemorrhagic anemia (D62)

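### Section 9.7.1 names ischemic stroke, not the primary stroke/systemic embolism composite, in the Kaplan-Meier sentence of the primary-outcome analysis

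*Combined protocol and SAP*

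**What the plan says.** Section 9.1 lists "Primary outcome: stroke and systemic embolism", and section 9.3.2.1 repeats it: "Outcome name: stroke and systemic embolism". Section 8 frames the primary objective on the same composite, and section 9.5 plans precision on a stroke/SE event rate.

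Within that composite, the stroke condition in section 9.3.2.1 is "Diagnosis of stroke defined as I60-I64 occurs in the same month as the imaging". Systemic embolism has its own algorithm in the same section.

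Section 9.7.1, under the primary-outcome subheading, estimates "The hazard ratio (HR) of stroke/systemic embolism for the dabigatran cohort as compared to the warfarin cohort" by Cox regression in the matched sample. The same paragraph ends with a Kaplan-Meier analysis showing numbers at risk, and adds that "the number of events for ischemic stroke and major bleeding will be provided". The secondary-outcome paragraph that follows says only that the same method will be used for major bleeding.

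The abstract says "Kaplan-Meier curves for event-free survival will be estimated" and does not name the event.

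**The concern.** The hazard ratio and the Kaplan-Meier output in one paragraph should describe the same endpoint, and here they do not. A programmer who follows the sentence literally would draw a curve for a narrower event than the one in the Cox model, and the primary hazard ratio would be printed beside it.

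In the visible plan, the Kaplan-Meier output is the only display of how events accrue over follow-up. If it shows ischemic stroke, a reader cannot see from it when stroke/SE events occurred in each arm, how many patients were still at risk for the composite, or whether one hazard ratio summarises the composite well.

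The programmer would also have to invent a definition. The visible text does not say which codes make up ischemic stroke as an outcome, how unspecified stroke (I64) is treated, whether the imaging plus rehabilitation-or-death rule still applies, or what happens to follow-up when a patient has a hemorrhagic stroke or systemic embolism first.

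**Working it through.** The check is mainly a comparison of text.

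**1. Endpoint by place in the document**

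| Place | Endpoint |
|---|---|
| Section 8, primary objective | stroke/SE |
| Section 9.1, outcomes | stroke and SE |
| Section 9.3.2.1, outcome name | stroke and SE |
| Section 9.5, planned event rate | stroke/SE |
| Section 9.7.1, Cox model | stroke/SE |
| Section 9.7.1, Kaplan-Meier sentence | ischemic stroke; major bleeding |
| Abstract, Kaplan-Meier line | not named |

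Only the Kaplan-Meier sentence in 9.7.1 departs from the composite.

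**2. Are the two endpoints the same in practice?** No. Section 9.3.2.1 codes stroke as I60-I64, and Table 3 as I61-64. Section 9.3.2.2 labels I60 as subarachnoid and I61 as intracerebral hemorrhage, so either range contains hemorrhagic stroke. Systemic embolism (I74, and retinal occlusion H34) lies outside any stroke code.

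**3. Is ischemic stroke defined as an outcome?** Not in the visible text. The term appears otherwise only as a history item in the risk scores (Tables 6 and 7). There the codes are I63, I64 and G45, with I74 added in one row, so they mix in TIA or systemic embolism. Cardioembolic stroke (I634) appears in Table 3 only as an anchor diagnosis for other algorithms. The table of contents shows redacted entries after 9.3.2.2 and after 9.7.1, so a definition may exist out of sight.

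**4. Where would each component be displayed if the sentence is followed?**

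| Component of the primary outcome | Ischemic-stroke curve | Major-bleeding curve |
|---|---|---|
| Ischemic stroke | yes | no |
| Hemorrhagic stroke, I60 or I61 | no | yes, if with hospitalization and/or transfusion |
| Hemorrhagic stroke, I62 | no | not listed by name, but the list is stated to be open |
| Unspecified stroke, I64 | not stated | no |
| Systemic embolism | no | no |

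**5. Size.** The total of planned primary events can be sketched from section 9.5. It uses 4,421 per group, 0.40487 years of follow-up, a rate of 0.03 per year and a hazard ratio of 0.716. I take the rate as the warfarin rate, which is an assumption because Table 9 does not name the arm.

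- Warfarin: 4,421 × 0.40487 × 0.03 = 53.7
- Dabigatran: 53.7 × 0.716 = 38.4
- Total: about 92

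If the rate were applied to both arms alike, the total would be 2 × 53.7 = about 107. Neither total can be carried further. The documents give no split into ischemic stroke, hemorrhagic stroke and systemic embolism, so the number missing from the stroke curve cannot be computed.

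**The case against.** The strongest reply is that the sentence can be parsed differently. The words naming ischemic stroke and major bleeding may attach only to the event counts, and the Kaplan-Meier analysis itself may take its endpoint from the subheading. The abstract's general line on event-free survival does not exclude stroke/SE either. This stands in part: the text does not rule out a stroke/SE curve, so a reader should not infer that the plan forbids one or contains no time-to-event display. But on this parsing the curve has no named endpoint and the counts beside it still belong to another one, so the sentence needs correcting on either reading.

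A reader might also infer that ischemic stroke is an undefined outcome. The documents support this only for the visible text, because of the redacted entries.

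A reader might infer that hemorrhagic strokes vanish from the figures altogether. They do not: I60 and I61 events with hospitalization and/or transfusion fall in the major-bleeding curve, though mixed with gastrointestinal and other bleeds.

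It is also tempting to say that absolute stroke/SE risk would go unreported, or that the omitted component is where the arms differ most. Section 9.7.1 gives incidence rates by cohort, and the abstract adds event counts, patient-years and confidence intervals. Those rates average over follow-up but do give absolute frequency. No passage gives effects by stroke type.

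Finally, pairing ischemic stroke with major bleeding, the other main outcome, suggests a slip for stroke/SE. That is likely. It makes the correction easy but does not make the text right.

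**Conclusion.** The Kaplan-Meier sentence is wrong as written. It names an endpoint that is not the primary outcome in the paragraph meant to specify the primary analysis. On its natural reading, no curve or number at risk is specified by name for the stroke/SE composite, and its event counts are for ischemic stroke.

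The effect is confined to one planned display. The Cox endpoint, the incidence rates and the precision planning all use stroke/SE and are untouched, and no hypothesis test depends on the curve. The size in events is unknown and cannot be derived from the documents.

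The conclusion that the endpoints differ rests on visible text alone and would stand even if a redacted section defined ischemic stroke. Only the statement that it lacks an outcome code list depends on what is redacted.

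**What to change.** In the Kaplan-Meier sentence of section 9.7.1, replace ischemic stroke with stroke/systemic embolism (primary outcome), so that curves, numbers at risk and event counts are given by treatment group in the matched sample for that composite and for major bleeding. Name the same two outcomes in the abstract's event-free survival line.

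If an ischemic-stroke curve is also wanted, add it as a separately defined component. Give its own code list, state how I64 is handled, say whether the imaging plus rehabilitation-or-death rule applies, and say how follow-up ends when another component occurs first.

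The stroke code range should be reconciled at the same time (I60-I64 in the text of 9.3.2.1, I61-64 in Table 3), because it decides which events enter both the curve and the hazard ratio.

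The main change costs one phrase and one figure. It uses the event times already derived for the Cox model, needs no new data, and has no real downside.

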9.8 QUALITY CONTROL

Milliman will conduct a quality check as below:

Calculation check: both of program codes for calculation and the data codes used the calculation will be checked by different person from that who calculated.

Pre-release peer review: comprehensive check on methodology, calculation process, and consistency of results will be performed by a qualified peer-reviewer.

Post-release peer review: comprehensive check on the project will be conducted by qualified peer-reviewer belonging to another office.

9.9 LIMITATIONS OF THE RESEARCH METHODS

- Unobservable factors or factors not captured in the database such as laboratory data not equally distributed in the treatment groups that may also influence the outcomes could lead to unobserved confounding.
- The anticipated sample size might be limited which might lead to imprecise results. Therefore the study can only be considered to be exploratory. Based on the expected small sample size there is also the risk of pure chance findings. No hypothesis testing is planned,
- All information of each patient is from consent giving DPC hospitals. If patients have visits to other non-DPC medical institutions, these data are not included in the MDV data.

9.10 OTHER ASPECTS

None

9.11 SUBJECTS

The source population is Japanese patients who have claims data in MDV commercial database. In order to have claims in the database, the patients must have received some medical intervention, out or in-patient hospital visit, or pharmacy prescription from the DPC hospitals in Japan. DPC hospitals are large hospitals, often associated with medical schools or government funding, providing both acute and chronic medical care in Japan. Compared to non-DPC hospitals, they tend to provide more specialized, intensive medical care in addition to outpatient primary care tending to chronic disease requiring non-urgent care. MDV database has contractual agreement to receive claims data from approximately 12% of all DPC hospitals in Japan, and the selection is based on the willingness on the side of DPC hospitals to receive either financial compensation or data services from MDV. The inclusion and exclusion criteria are intended to select those Japanese atrial fibrillation patients who have non-valvular etiology and have newly initiated oral anti-coagulants for stroke prevention. The data cut-off of 14 Mar 2011 to 30 June 2016 is to select those claims that have occurred after the launch of dabigatran and to the most recent available data cut from MDV at the time of protocol writing.

9.11.1 Cases

Not Applicable

9.11.2 Controls

Not Applicable

9.12 BIAS

Unobservable factors or factors not captured in the database such as laboratory data not equally distributed in the treatment groups that may also influence the outcomes could lead to unobserved confounding.. In order to minimize bias, this study will include only new users (treatment-naïve initiators) of warfarin and dabigatran and use propensity score matching.

10. PROTECTION OF HUMAN SUBJECTS

As this is a study based on databases using anonymous and personally unidentifiable data; therefore protection of human subjects is not applicable for this study.

11. MANAGEMENT AND REPORTING OF ADVERSE EVENTS/ADVERSE REACTIONS

The outcomes of the study are the baseline characteristics (pre-treatment) and medication prescriptions.. This is a non-interventional study based on existing data, in which all patient data will be de-identified and analyzed in aggregate. Individual patient safety related information will not be captured during this study. Thus, individual safety reporting is not applicable for this study.

12. PLANS FOR DISSEMINATING AND COMMUNICATING STUDY RESULTS

A manuscript describing this work will be submitted for publication in a peer-reviewed journal.

Target of final study report (publication submission): Sep 2017

13.2 UNPUBLISHED REFERENCES

ANNEX 1. LIST OF STAND-ALONE DOCUMENTS

| Number | Document Reference Number | Date | Title |
|---------------|----------------------------------|-------------|--------------|
| | None | | |
| | | | |
| | | | |

ANNEX 2. ENCEPP CECKLIST FOR STUDY PROTOCOLS

None

